Appendix D Specific list for Glucocorticoid Toxicity Index

	At Baseline or Before	New Since Baseline
Body Mass Index - An absolute increase in BMI of more than 8 units (and >24.9 kg/m ²)		
Blood Pressure - Hypertensive emergency (see definition, below) - PRES (Posterior reversible encephalopathy syndrome) (see definition, below)		
Endocrine - Symptomatic adrenal insufficiency		
Bone Health - Osteonecrosis of one joint - Osteonecrosis of more than one joint - Bone mineral density decrease > 6% - Insufficiency fracture - Insufficiency fracture in more than one bone		
Muscle & Tendon - Severe glucocorticoid myopathy (see definition) - Tendon rupture - More than one tendon rupture		
Eye - Central serous retinopathy - New-onset or worsened elevation of intra-ocular pressure requiring treatment or change in treatment - Posterior subcapsular cataracts (or history of same)		

Infection 
- Grade 4 infection (see definition, below)- Grade 5 infection (death from infection)		
Glucose Tolerance 
- Diabetic nephropathy- Diabetic neuropathy- Diabetic retinopathy		
Gastrointestinal Tract 
- Gastrointestinal perforation (occurring in the absence of regular nonsteroidal anti-inflammatory drug use)- Peptic ulcer disease confirmed by endoscopy (excluding H. pylori)		
Skin 
- Severe skin toxicity (see definition, below)		
Neuropsychiatric 
- Psychosis, defined as hallucinations, delusions, or disorganized thought processes (occurring in the absence of mania, delirium, or depression)- Glucocorticoid-induced violence toward self or others		
Other glucocorticoid toxicities Please specify: _____ _____		

DEFINITIONS:

Hypertensive emergency: The blood pressure has reached levels that are damaging organs. Hypertensive emergencies generally occur at blood pressure levels exceeding 180 mmHg systolic OR 120 mmHg diastolic, but can occur at even lower levels in patients whose blood pressure have not been elevated before. Complications can include: stroke, loss of consciousness, memory loss, myocardial infarction, hypertensive retinopathy or nephropathy, aortic dissection, angina, pulmonary edema.

Posterior reversible leukoencephalopathy syndrome (PRES): A clinical radiological entity. Clinical features may include headaches, altered mental status, seizures, and visual loss, depending on the affected neuroanatomy. Characteristic Magnetic Resonance Imaging (MRI) findings include vasogenic edema involving the white matter that predominantly affects the posterior occipital and parietal lobes of the brain, although other brain regions may also be affected. Confirmation by MRI is required as is exclusion of other potential causes (including hypertensive emergency).

Severe glucocorticoid myopathy: Grade 3 or worse myopathic weakness or respiratory myopathic weakness attributable to glucocorticoid myopathy.

Central serous retinopathy: a fluid detachment of macula layers from their supporting tissue. Requires formal ophthalmology examination, typically accompanied by optical coherence tomography and/or fluorescein angiography for diagnostic confirmation.

Grade 4 infection: Life-threatening consequences (e.g., septic shock, hypotension, acidosis, necrosis).

Diabetic nephropathy: Macroalbuminuria; i.e., a urinary albumin excretion > 300 mg in a 24-hour collection or a urinary protein: creatinine ratio > 300mg/g.

Diabetic neuropathy: Any of four types of peripheral neuropathy occurring in the setting of diabetes mellitus, namely: 1) a distal sensory polyneuropathy; 2) autonomic neuropathy (hypoglycemia unawareness, bladder or bowel problems, erectile dysfunction, and other autonomic nervous system issues); 3) diabetic amyotrophy (muscle infarction); or 4) mononeuritis (e.g., foot drop attributed to diabetic neuropathy).

Diabetic retinopathy: Any form of retinopathy associated with diabetes mellitus, including both non-proliferative and proliferative forms of diabetic retinopathy as well as diabetic macular edema. These complications must be confirmed by an ophthalmologist.

Severe skin toxicity: Any of the three following manifestations:

Grade 4 acneiform lesions - Papules and/or pustules covering any % body surface area (BSA), which may or may not be associated with symptoms of pruritus or tenderness and are associated with extensive superinfection with IV antibiotics indicated or life-threatening consequences

Grade 3 striae - Covering >30% BSA or associated with ulceration

Grade 3 ulcers - Combined area of ulcers >2 cm or full-thickness skin loss involving damage to or necrosis of subcutaneous tissue that may extend down to fascia

References

Appendix E FACIT Fatigue Scale (Version 4) (Paper Version)*

[figure not shown]

[figure not shown]
*This version will be adapted for use in the electronic format.

Appendix F EuroQol Questionnaire (EQ-5D-3L) (Paper Version)*

[figure not shown]
US (English) © 1998 EuroQol Group. EQ-5D™ is a trade mark of the EuroQol Group

[figure not shown]

[figure not shown]
- *This version will be adapted for use in the electronic format.

[figure not shown]
Appendix G SF-36 (Version 2) (Paper Version)*

[figure not shown]

[figure not shown]
SF-36v2® Health Survey © 1992, 1996, 2000 Medical Outcomes Trust and QualityMetric Incorporated. All rights reserved.
SF-36® is a registered trademark of Medical Outcomes Trust.
(SF-36v2® Health Survey Standard, United States (English))

[figure not shown]

[figure not shown]

*This version will be adapted for use in the electronic format.

Appendix H Health Assessment Questionnaire (HAQ-DI) (Paper Version)*

Your PAIN: How much pain have you had IN THE PAST WEEK:

Place a vertical (I) mark on the line to indicate the pain

No pain
0 mm

Severe pain
100 mm

Your HEALTH: Please rate how well you are doing on a scale of 0 to 100 (0 represents “very well” and 100 represents “very poor” health)

Please place a vertical mark (I) on the line below to indicate how well you are doing.

Very well
0 mm

Very poor
100 mm

*This version will be adapted for use in the electronic format.

Appendix I Physician's Global Assessment of Disease Activity (Paper Version)*

PHYSICIAN'S GLOBAL ASSESSMENT OF DISEASE ACTIVITY

Place a vertical mark on the line for how you would assess your patient's current disease activity

A horizontal line with vertical end caps, representing a scale for disease activity assessment. The left end is labeled "Not active" and "0 mm". The right end is labeled "Very active" and "100 mm".

*This version will be adapted for use in the electronic format.

Appendix J GCA Biomarker Objectives

The objectives of the Precision Medicine Plan are to characterize the disease activity of GCA patients while on steroid taper or sarilumab treatment. Both treatment arms will be exposed to anti-inflammatory agents so evaluation of baseline inflammation and changes over time will be evaluated using comprehensive approaches to evaluating circulating immune cell types, circulating proteins and evaluation of gene expression changes.

Whole blood for immunophenotyping of circulating immune cells

The contribution of the innate and adaptive immune systems to GCA disease activity and treatment response are not well understood. In order to better characterize alterations of the innate and adaptive immune system predose and after steroid taper or sarilumab treatment, whole blood collections at predose at V2, V4 and V9 are proposed to characterize T cell subsets that are purported to be dysregulated in patients and that may not be controlled by steroids CD4 (Treg, Th1, Th17), CD8 (cytotoxic lymphocytes) ¹⁻⁵ or cells that produce or are activated by IL6 signaling (monocytes ⁶, B cells ⁸ respectively). In total 120 patients will be selected via IRT for this analysis, please refer to Lab Manual in detail

- 40 patients each in Group A and Group D
- 20 patients each in Group B and Group C

Optional Future Biomarker Serum and Plasma for circulating protein analysis

The purpose of banking serum and plasma is to analyze proteins at baseline and after treatment that may be associated with disease progression, severity and treatment response to anti IL-6R therapy. Although acute phase reactants have been well described in GCA patients, proteins that associate with overlapping PMR symptoms of morning stiffness and shoulder and hip pain have not been explored in the other studies. Proteins that may be explored but not limited to the following: proteins involved in the IL6 signaling pathway (IL-6, soluble IL-6R, fibrinogen, serum amyloid A etc), synovitis and bursitis (adhesion and proteases ^{9,10}), cytokines involved in TH1/Th17 pathway and the HPA axis (cortisol).

Optional Pharmacogenetics analysis for DNA and RNA

DNA will be collected at a single visit to analyze the sequence to determine if there are genetic variants that predict disease flare, remission or response to anti-IL-6R therapy. RNA will be collected predose at V2 and then predose at V3 2 weeks after the first study drug administration to determine if anti-IL6R therapy changes gene expression patterns in circulating blood cells compared to steroid taper + placebo. DNA and RNA samples for the genomics sub-study will be double-coded as defined by the International Council for Harmonisation (ICH) guideline E15. Sub-study samples will be stored for up to 15 years after the final date of the database lock and may be used for research purposes. The purpose of the genomic analyses is to identify genomic associations with clinical or biomarker response, other clinical outcome measures and possible AEs. In addition, associations between genomic variants and prognosis or progression of as well

as related diseases may also be studied. These data may be used or combined with data collected from other studies to identify and validate genomic markers related to the study drug or and related diseases. Analyses may include sequence determination or single nucleotide polymorphism studies of candidate genes and surrounding genomic regions. Other methods, including whole-exome sequencing, whole-genome sequencing, DNA copy number variation, and transcriptome sequencing may also be performed. The list of methods may be expanded to include novel methodology that may be developed during the course of this study or sample storage period.

[figure not shown]
References:

1. Deng et al 2010
2. Visvanathan et al, 2011
3. Corbera-Bellata 2015
3. Samson et al., journal of autoimmunity 2016
4. Samson et al. 2012;
5. Miyabe et al. Annu Review Rheum. 2017
6. Van Sleen et al, Nature Scie Rep 2017 7:6553
7. Nadkarni et al Circ Cell. 2014
8. Alegria et al, Rheumatology 2016
9. Ribbens 2002 ARD 61:161
10. Kim 2013 J Bone Joint Surg Am. 20;95(4):e181-8

Appendix K Procedure for collection, handling, storage, and shipment of SAR153191 specimens for pharmacogenetic samples

Detailed information regarding collection, handling, storage, shipments of pharmacogenetics samples will be provided as separate lab manual.

Appendix L General guidance for the follow up of laboratory abnormalities by Sanofi

[figure not shown]
Note:

•The procedures described in the above flowchart are to be discussed with the patient only in case the event occurs. If applicable (according to local regulations), an additional consent (e.g., for HIV testing) will only be obtained in the case the event actually occurs.

•For individuals of African descent, the relevant value of concern is $<1000/\text{mm}^3$

Neutropenia is to be recorded as an AE only if at least 1 of the criteria listed in the general guidelines for reporting AEs in [Section 10.5.3](#) is met.

[figure not shown]
THROMBOCYTOPENIA

Note:

The procedures above flowchart are to be discussed with the patient only in case described in the the event occurs. If applicable (according to local regulations), an additional consent (e.g., for HIV testing) will only be obtained in the case the event actually occurs.

[figure not shown]
Thrombocytopenia is to be recorded as an AE only if at least 1 of the criteria listed in the general guidelines for reporting AEs in [Section 10.5.3](#) is met.

- In **ANY CASE**, **FOLLOW** the instructions #1 to #8 listed in the box below.
1. **INFORM** the medical monitor/CRA
 2. **COMPLETE** the specific form for “Liver Injury”
 3. **INVESTIGATE** specifically for malaise with or without loss of consciousness, dizziness, and/or hypotension and/or episode of arrhythmia in the previous 72 hours; rule out muscular injury
 4. **PERFORM** the following tests:
 - LFTs: AST, ALT, alkaline phosphatase, total and conjugated bilirubin, and prothrombin time /INR
 - CPK, serum creatinine, complete blood count
 - Anti-HAV IgM, anti-HBc IgM, anti-HCV and HCV RNA, anti-CMV IgM and anti-HEV IgM antibodies
 - Auto-antibodies: antinuclear, anti-DNA, anti-smooth muscle, anti-LKM
 - Depending on the clinical context, check for recent infection with EBV, herpes viruses, and toxoplasma
 - Hepatobiliary ultrasonography (can be completed by other imaging investigations if needed)
 5. **CONSIDER** consulting with hepatologist
 6. **CONSIDER** patient hospitalization if INR >2 (or PT <50%) and/or central nervous system disturbances suggesting hepatic encephalopathy
 7. **MONITOR** LFTs
-If investigational medicinal product is discontinued due to ALT increases as closely as possible to every 48 hours until stabilization, then every 2 weeks until return to normal (<2 x ULN) or baseline for at least 3 months, whichever comes last
 8. **FREEZE** serum (5 mL x 2)
 9. **In case of SUSPICION of GILBERT Syndrome**, a DNA diagnostic test could be proposed

Note: in addition, as soon as a seriousness criterion is met, the event should be notified within 24 hours to the monitoring team

INCREASE IN SERUM CREATININE

Increase in serum creatinine is to be recorded as an AE only if at least 1 of the criteria listed in the general guidelines for reporting AEs in [Section 10.5.3](#) is met.

Appendix M List of opportunistic infections

- Aspergillosis
- Blastomyces dermatitidis (endemic in the south-eastern and south-central United States, along Mississippi and Ohio rivers)
- Systemic candidiasis and extensive cutaneous cases
- Coccidioides immitis (endemic Southwestern US and Central and South America)
- Cryptococcus infection
- Cytomegalovirus infection
- Herpes simplex (severe/disseminated)
- Herpes zoster infection
- Histoplasmosis (pulmonary or disseminated; most common tropical areas Tennessee-Ohio-Mississippi river basins)
- Listeriosis
- Malaria (developing world)
- Infection with mycobacterium avium and other non-TB mycobacteria
- Pneumocystis Carinii pneumonia (PCP)

This list is indicative and not exhaustive

Appendix N Definition of Anaphylaxis

“Anaphylaxis is a serious allergic reaction that is rapid in onset and may cause death.”

(Adapted from *Sampson HA, Munoz-Furlong A, Campbell RL, Adkinson NF, Bock SA, Branum A, et al. Second symposium on the definition and management of anaphylaxis: Summary report—Second National Institute of Allergy and Infectious Disease/Food Allergy and Anaphylaxis Network symposium. J Allergy Clin Immunol 2006;117:391-7*)

Clinical criteria for diagnosing anaphylaxis

Anaphylaxis is highly likely when any one of the following 3 criteria are fulfilled:

1. Acute onset of an illness (minutes to several hours) with involvement of the skin, mucosal tissue, or both (eg, generalized hives, pruritus or flushing, swollen lips-tongue-uvula)
AND AT LEAST ONE OF THE FOLLOWING
 - a. Respiratory compromise (eg, dyspnea, wheeze-bronchospasm, stridor, reduced PEF, hypoxemia)
 - b. Reduced BP or associated symptoms of end-organ dysfunction (eg, hypotonia [collapse], syncope, incontinence)
 2. Two or more of the following that occur rapidly after exposure to a *likely allergen for that patient* (minutes to several hours):
 - a. Involvement of the skin-mucosal tissue (eg, generalized hives, itch-flush, swollen lips-tongue-uvula)
 - b. Respiratory compromise (eg, dyspnea, wheeze-bronchospasm, stridor, reduced PEF, hypoxemia)
 - c. Reduced BP or associated symptoms (eg, hypotonia [collapse], syncope, incontinence)
 - d. Persistent gastrointestinal symptoms (eg, crampy abdominal pain, vomiting)
 3. Reduced BP after exposure to *known allergen for that patient* (minutes to several hours):
 - a. Infants and children: low systolic BP (age specific) or greater than 30% decrease in systolic BP*
 - b. Adults: systolic BP of less than 90 mm Hg or greater than 30% decrease from that person's baseline
-

PEF, Peak expiratory flow; *BP*, blood pressure.

*Low systolic blood pressure for children is defined as less than 70 mm Hg from 1 month to 1 year, less than (70 mm Hg + [2 × age]) from 1 to 10 years, and less than 90 mm Hg from 11 to 17 years.

Appendix O Country-specific Requirements

Not applicable.

Appendix P Protocol Amendment History

Not applicable.

IMP:	investigational medicinal product
LDH:	lactate dehydrogenase
LDL-C:	low density lipoprotein cholesterol
LLN:	lower limit of normal
LLOQ:	lower limit of quantification
LLT:	lower level term
MD-VAS:	physician global assessment of disease activity- visual analog scale
MedDRA:	Medical Dictionary for Regulatory Activities
NCEP ATPIII:	National Cholesterol Education Program Adult Treatment Panel III
PRO:	patient reported outcome
PT:	preferred term
RBC:	red blood cell
SAEs:	serious adverse events
SF-36v2:	short form 36 version 2
SOC:	system organ class
TEAE:	treatment-emergent adverse event
ULN:	upper limit of normal
WBC:	white blood cell
WHO-DD:	World Health Organization - Drug Dictionary

1 OVERVIEW AND INVESTIGATIONAL PLAN

This statistical analysis plan (SAP) provides a comprehensive and detailed description of statistical strategy and methodology to be used to analyze the data from sarilumab EFC15068 study in patients with giant cell arteritis (GCA).

Due to the ongoing pandemic of COVID-19 (the disease caused by the novel coronavirus), the operations of sarilumab (Kevzara®) clinical trial EFC15068 have been significantly disrupted in various countries and sites. Consequently, the screening/recruitment activities for this study have been suspended since 19th of March 2020. Due to the protracted recruitment timeline and internal portfolio reprioritization, in July 2020, Sanofi has decided not to re-open the screening/recruitment activities and to discontinue the study. This decision is not related to any safety issues arising from the administration of sarilumab.

A total of 83 patients (out of 360 planned patients) have been randomized in the study. While the number of randomized patients may not be adequate to demonstrate a statistically significant benefit, the data generated from the treated patients may contribute to the further understanding of IL-6 signaling blockade in this disease state.

1.1 STUDY DESIGN AND RANDOMIZATION

Original study design

This is a multicenter, randomized, double-blind, placebo controlled 52-week Phase 3 study with a 24-week post-treatment follow up phase, evaluating the efficacy and safety of sarilumab in patients with giant cell arteritis (GCA).

Approximately 360 patients with GCA (new onset or refractory [eg, disease relapse] GCA) who meet the entry criteria will be randomized to 4 parallel treatment groups with sarilumab 200 mg q2w, 150 mg q2w, or placebo q2w plus 26-week prednisone taper, or placebo q2w with 52-week standardized prednisone taper at a ratio of 2:1:1:2 as described below. Randomization will be stratified by the starting dose of prednisone at baseline (<30 mg/day or ≥30 mg/day) using a block randomization schedule, and aim to enroll at least 30% of new onset patients by capping enrolment of refractory patients to ≤70% of total patients randomized.

- Treatment Group A: sarilumab 200 mg q2w with a 26-week taper of CS.
- Treatment Group B: sarilumab 150 mg q2w with a 26-week taper of CS.
- Treatment Group C: sarilumab matching placebo q2w with a 26-week taper of CS.
- Treatment Group D: sarilumab matching placebo q2w with a 52-week taper of CS.

It is important to optimize CS treatment prior to randomization to minimize the risk of adverse sequelae from GCA. Patients will be dosed with prednisone between 20 to 60 mg/day at the time of randomization (baseline) and initiate a taper according to the protocol defined schedule. Patients will be initiated on a standardized taper of prednisone from the time of randomization.

The taper will initially be open label; patients will have between 1 to 7 weeks to taper prednisone dose to 20 mg/day following randomization.

The further tapering of prednisone once a dose of 20 mg/day is achieved will be done in a blinded manner. To achieve the appropriate daily dose during this phase, patients will receive a combination of prednisone and/or placebo to prednisone depending on the assigned treatment group and associated taper regimen.

The total tapering period (open label plus double blind prednisone periods) will be between 46 weeks to 52 weeks depending on the initial prednisone dose at randomization.

At each site visit, the patient's disease will be assessed to determine whether the patient can adhere to the protocol defined prednisone taper schedule.

During the course of study, for patients in need of rescue therapy as per Investigator judgment, CS should be the agent of first choice. Patients may continue SC administration of sarilumab or matching placebo only if CS is used as the rescue therapy. If the patients remain symptomatic despite CS rescue therapy, then other treatment options including nonbiological immunosuppressive drugs may be used and the patient must be discontinued from the study treatment and considered a non-responder.

If the patient or Investigator decides to discontinue the administration of blinded sarilumab injections, then the patient will be asked to return to the site for study assessments as per protocol until end of study (EOS) evaluation, unless the patient cannot or does not wish to continue the assessments, in which case an early withdrawal visit and safety follow up should be performed. It is recommended that patients complete Visit 13, if possible.

Total duration of study participation for each patient is up to 82 weeks:

- Up to 6 weeks screening period.
- 52-week treatment period (sarilumab or placebo, double-blind phase).
- 24-week post treatment follow-up period.

The last patient last visit will occur when the last patient has completed the 24-week follow up period (EOS). The end of the clinical trial is defined as the last patient's last visit.

Study discontinuation plan

As mentioned in [Section 1](#), due to the protracted recruitment timeline and internal portfolio reprioritization, Sanofi has decided to terminate the EFC15068 study in July 2020. For patients who were already enrolled with ongoing treatment in the study, investigators were instructed to discontinue the study drugs and transition these patients into post-treatment follow-up period for safety assessments. The study discontinuation plan is as follows:

- All randomized patients should stop by 12 weeks from the date of announcement to the sites and should be scheduled for the end of study treatment visit at their earliest

convenience and no later than *October 13, 2020*, which would ensure sufficient time for patients to identify alternative therapy as needed.

- All patients will have a follow-up (EOS) visit that is 6 weeks after treatment cessation and no later than *November 24, 2020*.

Thus, the last patient last visit will occur when the last patient has completed the 6-week follow-up period (EOS). The end of the clinical trial is defined as the last patient's last visit.

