2.1.4 Safety endpoints

The safety analysis will be based on the reported adverse events (AEs), serious AEs (SAEs) and adverse events of special interest (AESIs) including but not limited to neutropenia, thrombocytopenia, elevations in hepatic enzymes leading to permanent discontinuation and

tuberculosis, and other opportunistic infections. Other safety information, such as clinical laboratory data and vital signs will also be assessed.

Observation period

The observation period will be divided into 4 epochs:

- The **screening** epoch is defined as the time from the signed informed consent date up to the time prior to first dose of SC IMP.
- The **treatment** epoch is defined as the time from the first dose of the IMP to the last dose of the SC IMP in the DB period +13 days.
- The **residual treatment** epoch is defined as the time from the end of TREATMENT epoch to the last dose of the SC IMP +60 days.

The **post-treatment** epoch is defined as the time after the last dose of SC IMP +60 days. The rationale of having “last dose of SC IMP +60 days” as the end of follow-up epoch is to capture the events observed within an approximately 5 half-lives of the last sarilumab SC IMP.

The treatment-emergent adverse event (TEAE) period includes both **treatment** and **residual treatment** epochs.

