2.1.4.1 Adverse events variables

Adverse event observation period

- Pre-treatment AEs are AEs that developed or worsened or became serious from the signed informed consent date up to first administration of SC IMP
- TEAEs are AEs that developed or worsened or became serious during the TEAE period
- Post-treatment AEs are AEs that developed or worsened or became serious during the post-treatment period

All AEs (including SAEs and AESIs) will be coded to a “LLT”, “PT”, “HLT”, “HLGT”, and associated primary “SOC” using the version of MedDRA currently in effect at Sanofi at the time of database lock.

The occurrence of AEs (including SAEs and AESIs) will be recorded from the time of signed informed consent until the end of the study.

Any SAE brought to the attention of the Investigator at any time after the end of the study for the patient and considered by him/her to be caused by the IMP with a reasonable possibility, should be reported to the monitoring team.

Adverse event of special interest (AESI)

Adverse events of special interest will be flagged in the database. The AESIs and its search criteria are listed in [Table 5](#) below:

Table 5 - Protocol defined AESIs and search criteria

AESI flag	Search criteria
Clinically significant infections including: 
 • Opportunistic infections • Tuberculosis • Infections requiring prolonged medication • Infections requiring parenteral treatment 	Reported by the investigators on the AE CRF page with AESI box ticked.
Lab abnormalities including: 
 • ALT increase leading to permanent discontinuation • ANC decrease leading to permanent discontinuation • Thrombocytopenia leading to permanent discontinuation 	
ALT >= 3xULN	
Pregnancy	CRF checkbox: Pregnancy
Overdose	CRF checkbox: Symptomatic Overdose

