2.4.5.1 Analyses of adverse events

Generalities

The primary focus of AE reporting will be on TEAEs. Pre-treatment and post-treatment AEs will be described separately.

If an AE date/time of onset (occurrence, worsening, or becoming serious) is incomplete, an imputation algorithm will be used to classify the AE as pre-treatment, or TEAE, or post-treatment AE. The algorithm for imputing date/time of onset will be conservative and will classify an AE as treatment-emergent unless there is definitive information to determine it is pre-treatment or post-treatment. Details on classification of AEs with missing or partial onset dates are provided in [Section 2.5.3](#).

Adverse event incidence tables will present by SOC, HLGT, HLT, and PT, sorted in SOC internationally agreed order and then alphabetical order, and present the number (n) and percentage (%) of patients experiencing an AE by treatment group. Multiple occurrences of the same event in the same patient will be counted only once in the tables within a treatment phase. The denominator for computation of percentages is the safety population within each treatment group.

The tables by primary SOC and PT will be sorted by internationally agreed order of SOC and decreasing frequency of PT within SOC. Sorting will be based on results for the sarilumab 200mg arm.

Analysis of all treatment-emergent adverse events

The following TEAE summaries will be generated for the safety population.

- Overview of TEAEs, summarizing number (%) of patients with any
 - TEAE
 - Serious TEAE
 - TEAE leading to death
 - TEAE leading to permanent treatment discontinuation
- All TEAEs by primary SOC, HLGT, HLT, and PT, showing number (%) of patients with at least one TEAE sorted by SOC internationally agreed order. The other level (HLGT, HLT, PT) will be presented in an alphabetic order.
- All TEAEs by primary SOC and PT, showing number (%) of patients with at least one TEAE, sorted by SOC internationally agreed order and decreasing incidence of PTs within SOC. This sorting order will be applied to all other tables, unless otherwise specified.
- All TEAEs by primary SOC, showing number (%) of patients with at least one TEAE, sorted by internationally agreed order of primary SOC.

- All TEAEs by relationship, presented by primary SOC, HLG, HLT, and PT, showing number (%) of patients with at least one TEAE, sorted by SOC internationally agreed order. The other level (HLG, HLT, PT) will be presented in an alphabetic order.

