2.4.5.2 Deaths

The incidence of death will be generated on the safety populations.

- Number (%) of patients who died by study period (on-treatment, treatment residual, and post-treatment).
- Death in non-randomized patients or randomized but not treated patients.
- TEAE leading to death (death as an outcome on the AE CRF page as reported by the Investigator) by primary SOC and PT, showing number (%) of patients sorted by internationally agreed order of SOC and decreasing frequency of PT within a SOC in the Sarilumab 200mg q2w treatment group.

Listings will be provided for all deaths with flags indicating during treatment or post-treatment status.

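### Most patients stopped under the discontinuation plan leave the study before the SAP's post-treatment epoch opens, yet post-treatment deaths are reported as a percentage of the whole safety population

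*SAP*

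**What the plan says.** SAP 1.1 (study discontinuation plan) applies to patients still on drug when the sponsor ended the study in July 2020: "For patients who were already enrolled with ongoing treatment in the study, investigators were instructed to discontinue the study drugs". The end-of-treatment visit is due by 13 October 2020. For the visit that ends participation, the plan says "All patients will have a follow-up (EOS) visit that is 6 weeks after treatment cessation", with a deadline of 24 November 2020. The plan does not say whether cessation means the last SC dose or the end-of-treatment visit.

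SAP 2.1.4.1 says that adverse events "will be recorded from the time of signed informed consent until the end of the study".

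SAP 2.1.4 sets the epochs. Treatment runs to 13 days after the last SC dose, and residual treatment from there to 60 days after it. The post-treatment "epoch is defined as the time after the last dose of SC IMP +60 days". The treatment-emergent period is treatment plus residual treatment, and the 60 days are meant to cover about five half-lives.

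SAP 2.4.5.2 summarises deaths on the safety population, including "Number (%) of patients who died by study period (on-treatment, treatment residual, and post-treatment". For adverse event tables, SAP 2.4.5.1 says: "The denominator for computation of percentages is the safety population within each treatment" group. It adds that post-treatment events will be described separately, and gives no other denominator for them.

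**The concern.** The epochs fit a design with 24 weeks of follow-up after Week 52. When follow-up fell to six weeks, the epochs and the denominators stayed as they were. A patient who leaves the study before day 60 after the last dose cannot have a post-treatment event recorded in the ordinary way, but still sits in the denominator. A low post-treatment death percentage would then partly reflect missing observation.

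The patients who do contribute post-treatment time are those who finished treatment well before the announcement and those who stopped SC drug early but stayed in the study. If early stopping differs by arm, the arms will differ in observed post-treatment time, and crude percentages will not show it. With planned group sizes of about 14 to 28 (SAP Table 1), one event is visible: 1/14 = 7.1%.

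The treatment-emergent window is also cut short for patients stopped under the plan, and the SAP does not say so.

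**Working it through.** **Inputs.** EOS six weeks after cessation; deadlines 13 October and 24 November 2020 (SAP 1.1). Post-treatment epoch opens after last SC dose + 60 days (SAP 2.1.4). Last SC dose at Week 50, end of treatment at Week 52 (D365), Visit 13 at D407, EOS at D532, visit windows ±3 days (flow chart). Dosing window ±3 days (Protocol 8.1.1). 83 randomised (SAP 1). 36 able to complete 52 weeks (SAP 2.3.1).

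**1. The plan's own figure.** 24 November minus 13 October 2020 = 42 days = 6 weeks. It reproduces.

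**2. Last dose to EOS.**
- Cessation = last SC dose: 42 days, which is 60 − 42 = 18 days short of the post-treatment epoch.
- Cessation = end-of-treatment visit two weeks after the last dose: 14 + 42 = 56 days, which is 4 days short.
- The second reading with windows, using the Week 50 dose (D351) and Visit 13 (D407) as the pattern: shortest (407 − 3) − (351 + 3) = 50 days; longest (407 + 3) − (351 − 3) = 62 days.

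**3. The original design, for contrast.** 532 − 351 = 181 days from last dose to EOS, leaving 181 − 60 = 121 days of post-treatment epoch.

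**4. Effect on a post-treatment percentage.** With d deaths, N in the safety population and k patients followed past day 60, the SAP reports d/N and the proportion among those observed is d/k. The ratio is N/k. The documents do not give k, so the values below are assumed, with N = 83 (the safety population cannot be larger) and one death:

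| k (assumed) | d/N | d/k | N/k |
|---|---|---|---|
| 36 | 1.2% | 2.8% | 2.3 |
| 20 | 1.2% | 5.0% | 4.2 |
| 10 | 1.2% | 10.0% | 8.3 |
| 5 | 1.2% | 20.0% | 16.6 |

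**5. Why 36 is only an illustration.** SAP 2.3.1 selects the 36 as randomised early enough to finish 52 weeks by October 2020. If the announcement came 12 weeks before 13 October 2020, it fell about 21 July 2020. A patient had to be randomised by about 23 July 2019 to reach D365 by then, and by about 7 June 2019 to pass last dose + 60 days on the original schedule. So some of the 36 fall under the six-week rule, which lowers k. Any of the other 47 who stopped early and stayed in the study raise it.

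**The case against.** The best case against has five parts.

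*Only the deaths line is explicit.* Every adverse event table listed in SAP 2.4.5.1 is treatment-emergent, and SAP 2 presents the follow-up phase only as needed. A reader might infer that a post-treatment adverse event percentage table is specified. It is not; the denominator there follows from the general rule. This stands.

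*Some plan patients may pass day 60.* A reader might infer that none can. The second reading of cessation reaches 62 days, and a missed final dose would lengthen the gap. This stands, so the claim is about most of these patients.

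*The size is unknown.* A reader might take 2.3 as a lower bound on the understatement. Step 5 shows that k could lie on either side of 36, and N may be below 83. This stands.

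*The truncation is small.* Taking 24 weeks of treatment, the treatment-emergent period is about 168 + 60 = 228 days, so losing 4 to 18 days is about 2% to 8% of it. Protocol 10.4.4 also accepted at least six weeks of safety follow-up after early stopping, alongside a 60-day window. That makes this the lesser part of the point, but the cut still needs stating.

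*Safety is descriptive and partly covered elsewhere.* Deaths are listed with flags, IMP-related SAEs learned of after study end remain reportable, and a common denominator lets period percentages add up. All true, but the flagged listing does not show time at risk and late SAE reporting is not systematic. A reader might also infer that the SAP will present a fall in events after treatment, or that the arms do differ in early stopping. It plans no comparison between epochs, and the documents hold no data on stopping by arm.

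**Conclusion.** The mismatch is real. On either nominal reading, EOS falls 4 to 18 days before the post-treatment epoch opens, and the SAP's denominator for post-treatment deaths includes patients with no time in that epoch. The percentage is too low by N/k with k unknown; 2.3 illustrates k = 36 of 83 and is neither an estimate nor a bound. The conclusion assumes that EOS visits follow the plan's timing and that patients are not systematically followed after EOS.

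No hypothesis test is affected. The correction is still worth making, because safety is a secondary objective and the documents already accept the principle. Protocol 11.4.3 promises exposure-adjusted event summaries, which SAP 2.4.5 omits and SAP 1.6 does not list as dropped. The patient-years in SAP 2.4.3.1 cover treatment exposure only. SAP 2.4.5 bases its laboratory abnormality percentages on patients assessed in the period, and SAP 2.3.1 limits Week 52 remission to patients who could reach Week 52. The safety epochs received no such adjustment.

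**What to change.** Derive, for each patient, the days followed in each epoch from the last SC dose date and the last study contact date. Then:

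- In SAP 2.4.5.1 and 2.4.5.2, show for each epoch and arm the number of patients with at least one day of follow-up and the patient-years observed.
- Report post-treatment deaths, and any post-treatment adverse events, as counts against those patients or that time, and not as percentages of the whole safety population.
- State in SAP 2.1.4 that the treatment-emergent window ends at EOS for patients stopped under the plan who leave before day 60, and say what cessation means for timing EOS.

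The cost is SAP wording and one derived variable; no new data are needed. The downside is that period percentages no longer share a denominator, so they will not add up to an overall percentage. The counts still will.
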